## I. Study Synopsis

TITLE:	Persona Outcomes Led Assessment Research in Total Knee Arthroplasty (POLAR Study)
SPONSOR:	Zimmer Inc., Warsaw, IN
PROTOCOL NUMBER	CSU2012-10K
STUDY OBJECTIVES	
The primary objective of this study is to obtain implant survivorship and clinical outcomes data for commercially available Persona fixed bearing implants used in primary total knee arthroplasty.
 
The assessments will include:
 
 
1. Implant survivorship based on removal of a study device.
 
2. Safety based on incidence and frequency of adverse events.
 
3. Clinical performance measured by overall pain and function, quality of life data, radiographic parameters and survivorship.
 

TARGET POPULATION:	Patients qualifying for primary total knee arthroplasty who meet the inclusion/exclusion criteria for study participation
STUDY DESIGN:	Prospective multicenter, non-controlled study of commercially available Zimmer Persona fixed bearing knee components
STUDY TYPE:	Post-market
SAMPLE SIZE:	A maximum of 15 U.S. sites contributing a maximum of 100 implanted Persona knees per site
LENGTH OF STUDY:	Five year study Follow-up clinical visits include 6 weeks, 6 months, 1 year, 2, 3, 4, and 5 years post-op.

INCLUSION/EXCLUSION CRITERIA:	
INCLUSION CRITERIA:
 

1. Patient is 18 to 75 years of age, inclusive

2. Patient qualifies for a primary total knee arthroplasty based on physical exam and medical history, including diagnosis of severe knee pain and disability due to at least one of the following:

a. Rheumatoid arthritis, osteoarthritis, traumatic arthritis, polyarthritis

b. Collagen disorders and/or avascular necrosis of the femoral condyle

c. Post-traumatic loss of joint configuration, particularly when there is patellofemoral erosion, dysfunction or prior patellectomy

d. Moderate valgus, varus, or flexion deformities

e. The salvage of previously failed surgical attempts that did not include partial or total knee arthroplasty of the ipsilateral knee

3. Patient has participated in this study-related Informed Consent process

4. Patient is willing and able to provide written Informed Consent by signing and dating the IRB or EC approved Informed Consent form

5. Patient is willing and able to complete scheduled study procedures and follow-up evaluations

6. Independent of study participation, patient is a candidate for commercially available Persona fixed bearing knee components implanted in accordance with product labeling

 
EXCLUSION CRITERIA:
 

1. Patient is currently participating in any other surgical intervention studies or pain management studies

2. Previous history of infection in the affected joint and/or other local/systemic infection that may affect the prosthetic joint

3. Insufficient bone stock on femoral or tibial surfaces

4. Skeletal immaturity

5. Neuropathic arthropathy

6. Osteoporosis or any loss of musculature or neuromuscular disease that compromises the affected limb

7. Stable, painless arthrodesis in a satisfactory functional position

8. Severe instability secondary to the absence of collateral ligament integrity

9. Rheumatoid arthritis accompanied by an ulcer of the skin or a history of recurrent breakdown of the skin

10. Patient has a known or suspected sensitivity or allergy to one or more of the implant materials

11. Patient is pregnant or considered a member of a protected population (e.g., prisoner, mentally incompetent, etc.)

12. Patient has previously received partial or total knee arthroplasty for the ipsilateral knee

--------------------------------------	-----------------------------------------------------------------------------------------------------------------------------------------------------------------------------------------------------------------------------------------------------------------------------------------------------------------------------------------------------------------------------------------------------------------------------------------------------------------------------------------------------------------------------------------------------------------------------------------------------------------------------------------------------------------------------------------------------------------------------------------------------------------------------------------------------------------------------------------------------------------------------------------------------------------------------------------------------------------------------------------------------------------------------------------------------------------------------------------------------------------------------------------------------------------------------------------------------------------------------------------------------------------------------------------------------------------------------------------------------------------------------------------------------------------------------------------------------------------------------------------------------------------------------------------------------------------------------------------------------------------------------------------------------------------------------------------------------------------------------------------------------------------------------------------------------------------------------------------------------------------------------------------------------------------------------------------------------------------------------------------------------------------------------------------------------------------------------------------------------------------------------------------------------------------------------------------------------------------------------------------------------------------------------------------------------------------------------------------------------------------------------------------------------------------------------------------------------------------------------------------------------------------------------------------------------------------------------------------------------------------------------------------------------------------------------------------------------

STUDY DEVICE:	Commercially available Persona fixed bearing knee components implanted in accordance with product labeling
OUTCOMES MEASURES:	2011 Knee Society Score EQ-5D Forgotten Joint Score
PERFORMANCE ASSESSMENTS:	Pain and function Quality of life Radiographic parameters Survivorship
STATISTICAL REPORTING:	Performance will be evaluated for pain, function, quality of life, and survivorship. Data will be summarized descriptively additional to evaluation of data on surgical technique and instrumentation. Categorical data (e.g., gender or race) will be summarized using counts and percentages with 95% Confidence Interval (CI) limit over the time period of interest. Continuous data, such as age, will be summarized by using means, medians, SD, minimum, maximum, and 95% CI over the time period of interest. Implant survival and return to function will be summarized using a Kaplan-Meier method and presented with rates (as percentages) and CI. Routine summaries of complication data is represented by frequencies and percentages. Sample size is based on a longitudinal data collection model and using survivability as the primary endpoint of interest. The attrition rate is assumed to be 10%

This protocol is written based on guidelines from ISO 14155 Standard for Clinical Investigation of Medical Devices For Human Subjects – Good Clinical Practice (i) and the ICH Guideline on Good Clinical Practice (ii), and is in accordance with US Code of Federal Regulations 21 CFR Parts 11, 50 and 56 (iii)

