**D. Subject Enrollment**

Once the Informed Consent has been signed and dated by the subject, the subject will be considered enrolled in the study. A unique case identification number (Case ID) will be assigned to each participating subject/knee (bilateral subjects will be assigned a unique case ID number for each knee). This unique case ID number will be used throughout the study for identification. Case ID numbers will be assigned consecutively in ascending order per site, with the starting number for a given site defined by Sponsor.

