3. EQ-5D
4. Knee Society Score
  - a. Surgeon completed
  - b. Patient completed
5. Physician Assessment of Post-op Radiographs
6. Adverse Event Report (as applicable)
7. Protocol Deviations (as applicable)
8. Study Completion (as applicable)

Subjects will be followed post-operatively for up to 5 years. Unless the study is otherwise closed, data will continue to be collected until the subject completes the study per the protocol, voluntarily withdraws from the study, is withdrawn from the study by the investigator, is lost to follow-up, undergoes revision to remove a study device, or expires. See Management of Incurrent Events (Section IX, Subsection D of this protocol) for additional details. Reason(s) for study completion must be documented on the Study Completion case report form.

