#### **2. Adverse Events**

An adverse event is any unfavorable or unintended sign, symptom, or disease associated with the use of the study device, whether or not related to the device. Adverse event is synonymous with complication or medical event.

See Section IX, Subsection E of this protocol for additional information regarding adverse event classifications. All medical events, regardless of classification, are required to be reported on the Adverse Event Report case report form. The completed Adverse Event Report case report form must be submitted to Sponsor in a timely manner. The Investigator or Designee will also promptly provide Sponsor with any additional requested information required for Sponsor to comply with regulatory requirements. If applicable per their reporting requirements, the Investigator or Designee will also report applicable adverse event(s) to their IRB or EC.

3. Revision

In the event that removal of one or more of the study knee components is necessary, the Investigator will determine the best treatment and/or revision method for the subject.

Prior to revision surgery, the Investigator or qualified Designee must document any significant radiographic findings related to the need for revision on the Physician Assessment of Postop Radiographs case report form. An Adverse Event case report form must be completed for those findings indicated by an asterisk on the Physicians Assessment of Postop Radiograph case report form.

Once the revision surgery has been completed, the Investigator or qualified Designee must complete an Adverse Event case report form as well as a Study Completion case report form terminating the subject from the study. For the study completion status, select “Study Prosthesis Removed”. This procedure also applies to partial revisions such as polyethylene exchange.

4. Investigator Withdrawal

The Investigator can choose to withdraw a subject from the study if the subject no longer meets study inclusion/exclusion criteria. The reason for the Investigator’s withdrawal of the subject must be documented on the Study Completion case report form.

5. Subject Withdrawal

Study subjects may choose to withdraw from the study at any time, for any reason. If possible, a final evaluation will be completed for any subject who no longer wishes to participate in the study. The reason for the subject withdrawal must be documented on the Study Completion case report form.

6. Lost to Follow-up

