A study subject will be considered lost to follow-up after they have missed a visit and attempts to locate and evaluate the subject using the procedure outlined below have failed. All attempts to contact the subject are to be documented in the subject’s medical record and on the Study Completion case report form. Missed visit(s) also must be documented using the Protocol Deviations case report form. The first three contact attempts should be made by telephone, with additional attempts as outlined in the following table:

If	Then
a response is not received after three (3) phone calls	the Investigator or Designee should send a letter to the subject explaining the follow-up agreement per the Informed Consent, and requesting a response from the subject.
all attempts to contact the subject are unsuccessful or the subject is contacted and chooses to withdraw from the study	a Study Completion case report form will be completed and will specify the reason the subject is no longer participating in this study.

7. Protocol Deviations

Investigators should not deviate from the study protocol. If a protocol deviation does occur, the deviation must be documented on the Protocol Deviation case report form and submitted to Sponsor. If applicable per their reporting requirements, the Investigator or Designee will also report applicable protocol deviations to their IRB or EC.

8. Study Termination

Study subject participation is expected to end upon completion of the subject's 5-year follow-up visit unless the subject voluntarily withdraws from the study, is withdrawn from the study by the Investigator, is lost to follow-up, undergoes revision to remove a study device, or expires. Reason(s) for study completion must be documented on the Study Completion case report form.

If Sponsor decides to terminate the study early, Sponsor will inform the Investigators of the reason for early study termination. It is the responsibility of the Investigators to inform their IRB or EC as applicable according to local and national laws/regulations.

9. Modification of the Protocol

All amendments to this clinical protocol shall be agreed to by Sponsor and be recorded with a justification for the amendment prior to implementation. Approval of the applicable IRB or EC must be obtained prior to implementation, if required according to the local and/or national laws/regulations.

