**A. General Statistical Methods**

Statistical methodology will consist of summarizing collected data descriptively. Categorical data (e.g., gender or race) will be summarized using counts and percentages, and 95% Confidence Interval (CI), over the time periods of interest. Continuous data, such as age, will be summarized by using means, medians, standard deviation, minimum, maximum, and 95% CI over the time periods of interest. Implant survival and return to function will be

summarized using a Kaplan-Meier method and presented with rates (as percentages) and confidence intervals.

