**B. *Sample Size***

Sample size is based on a longitudinal data collection model and using survivability as the primary endpoint of interest. The attrition rate is assumed to be 10%.

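### Return to function is planned as a Kaplan-Meier rate with no stated rule for knees whose device is removed, or whose patient dies, before return; ordinary censoring would slightly overstate it

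*Combined protocol and SAP*

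**What the plan says.** The Statistical Reporting row of the synopsis gives implant survival and return to function one method: "Implant survival and return to function will be summarized using a Kaplan-Meier method and presented with rates (as percentages) and CI". Section XI.A repeats it; both are to be "summarized using a Kaplan-Meier method and presented with rates (as percentages) and confidence intervals". These are the only two places where return to function is mentioned. Neither gives an instrument, a threshold or a visit that would define the event, and neither states a censoring rule or names a competing-event method.

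Other sections fix when observation of a knee stops. Section VIII.L continues data collection until, among other reasons, the subject "is lost to follow-up, undergoes revision to remove a study device, or expires". Section IX.D, item 8 (Study Termination) has a matching list: "is withdrawn from the study by the Investigator, is lost to follow-up, undergoes revision to remove a study device, or expires". Item 3 (Revision) requires, after revision surgery, an adverse event form "as well as a Study Completion case report form terminating the subject from the study", and adds: "This procedure also applies to partial revisions such as polyethylene exchange".

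Section XI.B bases the sample size on "using survivability as the primary endpoint of interest". It gives no expected removal rate. Section XI describes all summaries as descriptive and allows their use in regulatory submissions and publications.

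**The concern.** One method is assigned to two endpoints that relate to removal in opposite ways. For implant survival, removal is the event, and Kaplan-Meier handles it correctly. For return to function, removal before return means that the knee can no longer return with the study device, and it also ends observation.

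A Kaplan-Meier curve that censors the knee at removal treats it as if it could still return at the same rate as the knees still followed. Its share is in effect passed on to those knees. Death before return works in the same way.

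At stake is the accuracy of one planned rate and its confidence interval. Pain and function are part of the clinical performance assessment in Section IV. The error can go only one way, towards a more favourable result, and more knees do not reduce it.

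**Working it through.** The plan gives no return rate, removal rate or precision target, so there is no figure of its own to reproduce. The check is of direction, then of size under stated assumptions.

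**Direction.** Let λ(u) be the rate of first return among knees not yet returned, S(u) the corresponding probability of not having returned if no removal occurred, and G(u) the probability that an unreturned knee has not been removed by time u.

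- Kaplan-Meier return with removal censored: 1 − S(t) = ∫ λ(u) S(u) du.
- Share actually returned with the device in place: ∫ λ(u) S(u) G(u) du.

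Since G(u) ≤ 1, the first is never below the second. They are equal only if no removal precedes a return that would otherwise have occurred by t.

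**Size at 1 year.** Assumed inputs, none from the documents:

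- Kaplan-Meier return at 1 year p = 0.90 or 0.80, with constant hazard L = −ln(1 − p), giving 2.303 or 1.609 per year.
- Total removal over 5 years R = 1%, 3% or 5%.
- Removal hazard m after return and h·m before return, with h = 1 (equally likely) or h = 5 (five times as likely before return).

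With a = L + h·m, m is solved from

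1 − R = exp(−5a) + L·exp(−5m)·[1 − exp(−5(a − m))]/(a − m),

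which for h = 1 reduces to m = −ln(1 − R)/5. The actual share returned at 1 year is (L/a)·(1 − exp(−a)), and the gap is p minus that share.

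Two cases in full, both with p = 0.90 and R = 5%:

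- h = 1: m = −ln(0.95)/5 = 0.01026; a = 2.3128; share = (2.3026/2.3128)·(1 − 0.0990) = 0.8970; gap 0.30 points.
- h = 5: m = 0.00763, h·m = 0.0381; a = 2.3407; share = (2.3026/2.3407)·(1 − 0.0963) = 0.8890; gap 1.10 points.

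| Return at 1 year (Kaplan-Meier) | Removal over 5 years | Gap, h = 1 (points) | Gap, h = 5 (points) |
|---|---|---|---|
| 90% | 1% | 0.06 | 0.22 |
| 90% | 3% | 0.18 | 0.65 |
| 90% | 5% | 0.30 | 1.10 |
| 80% | 1% | 0.06 | 0.20 |
| 80% | 3% | 0.18 | 0.60 |
| 80% | 5% | 0.30 | 1.01 |

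**Death.** At an assumed 1% per year, independent of return and as the only competing event, a = 2.303 + 0.01 = 2.313 for p = 0.90. The share is (2.303/2.313)·(1 − exp(−2.313)), and the gap is 0.29 points at 1 year.

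**Visit-based cross-check.** Assume Kaplan-Meier return of 40%, 75% and 90% at 6 weeks, 6 months and 1 year, with 0.5%, 1% or 2% of knees removed before return, split equally over the three intervals. If removals come before each interval's returns, the gap is 0.39, 0.78 or 1.56 points. If they come after, it is 0.24, 0.48 or 0.96. Timing within the interval therefore matters, and the first set is the upper case.

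**Comparison with sampling error.** The 95% half-width at 90% is 1.96·√(0.9·0.1/n). With 15 × 100 × 0.9 = 1,350 knees it is 1.60 points; with 6 × 100 × 0.9 = 540 knees it is 2.53 points. Both assume that every site fills its 100-knee cap and that the 10% attrition is a total; fewer knees give wider intervals. Every 1-year gap above lies inside these half-widths.

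**The case against.** The strongest reply is that the plan is silent rather than wrong. Ending follow-up is a rule about data collection, not about censoring. An analyst could keep a knee removed before return in the risk set as not returned, and then no bias arises. This stands: a reader might infer that the plan prescribes censoring at removal, but no section says so. The point is therefore conditional on Kaplan-Meier being used in its ordinary way. It survives because Kaplan-Meier is the only method named and nothing in the plan points to another handling.

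A second reply is that the missing event definition is the larger gap, since without it the bias cannot be sized from the documents. That is fair, and the definition comes first in the fix.

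A third is that the effect is small, on a descriptive summary in an uncontrolled study, and that removals are visible anyway in the survivorship curve and the complication counts. This also stands, and it limits the point to a minor one. It does not make the rate correct.

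Two stronger readings are not supported. A reader might infer that the primary endpoint is biased too; it is not affected through this route, because removal is its event. A reader might also carry the calculation to 5 years. The constant hazard used here would force Kaplan-Meier return at 5 years to 99.97% (1 − 0.20^5) or 99.999% (1 − 0.10^5), which is not credible, so it gives no usable 5-year size. Later gaps depend on a long-term return profile that the documents do not give, and the 1-year figures do not bound them.

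**Conclusion.** The point holds as a minor, inexpensive improvement. If knees removed before return are censored, the return-to-function rate is at or above the share that actually returns with the study device in place. That direction needs no assumption about rates.

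The size does. With 1–5% removal over 5 years, 80–90% return at 1 year and constant hazards, the 1-year overstatement is about 0.06–0.30 points when removal is equally likely before and after return. It is about 0.2–1.1 points when removal is five times as likely before. Censoring deaths would add to this. A higher removal rate, or a stronger concentration of removals in knees that have not recovered, would give a larger gap.

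**What to change.** In the Statistical Reporting row of the synopsis and in Section XI.A:

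1. Keep Kaplan-Meier for implant survival.
2. Define the return-to-function event by instrument, threshold and visit.
3. Summarize return to function by cumulative incidence, with device removal (partial revisions included) and death before return as competing events. Alternatively, keep those knees in the denominator as not returned to the end of follow-up, which serves the same purpose.

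The cost is one definition and one analysis rule. No new data collection is needed: removals are already recorded on the adverse event and study completion forms, and the survivorship curve needs the removal date in any case. The protocol text does not list the forms' date fields, so it is worth confirming that the date is captured. The downside is a slightly less favourable return-to-function rate.

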### IV. Study Objectives

The objective of this study is to obtain clinical performance (outcomes) data and survivorship for commercially available *Persona* fixed bearing knee components implanted in primary total knee arthroplasty. This will be done by analysis of validated outcome measurement tools, radiographs and adverse event data.

The assessments will include:

1. Implant survivorship based on removal of a study device
2. Safety based on incidence and frequency of adverse events
3. Clinical performance measured by overall pain and function, quality of life data, radiographic parameters and survivorship

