## VI. Study Population

Study population for primary statistical analysis will be comprised of males and females who require primary total knee arthroplasty and satisfy the inclusion/exclusion criteria outlined in this section of the protocol. In order to avoid potential selection bias, each Investigator will offer study participation to each consecutive patient presenting as a candidate for primary total knee arthroplasty using the commercially available (FDA cleared) *Persona* fixed bearing knee system. Candidates who express interest in study participation will be offered Informed Consent.

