**E. Determination of Eligibility**

Once Informed Consent has been obtained, the subject's eligibility to continue study participation will be determined by the study inclusion/exclusion criteria. This may include an interview to assess significant subject medical/surgical history, history of present illness/injury, evaluation of present pain and functional capacity, and a radiographic assessment. Evaluation of the inclusion/exclusion criteria will be documented on the Inclusion/Exclusion Criteria case report form. Subjects that do not meet all inclusion/exclusion criteria will be terminated from the study and no further study data will be collected. A Study Completion form will be completed and the reason for termination must be specified on the form. These subjects will be excluded from the primary statistical analysis for this study.

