**J. Intention to Treat**

Subjects who are enrolled in the study with an intention to treat (i.e. underwent the study Informed Consent process, signed and dated the Informed Consent, and met the study inclusion/exclusion criteria), but do not undergo the study surgery due to subject withdrawal, investigator withdrawal, or any other reason(s), will be terminated from the study. A Study Completion form will be completed and the reason for termination must be specified on the form. These subjects will be excluded from the primary statistical analysis for this study.

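### Adverse events are summarised only as crude percentages with no stated base or time horizon, which can read low in early interim reports (minor)

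*Combined protocol and SAP*

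**What the plan says.** Safety is one of three stated assessments: "Safety based on incidence and frequency of adverse events" (Section IV, and likewise the Synopsis). One sentence in the whole document gives a method for complications, in the Statistical Reporting row of the Synopsis: "Routine summaries of complication data is represented by frequencies and percentages". Section XI.A does not repeat it. It has only a general rule for categorical data (counts, percentages and a 95% confidence interval by time period), illustrated with gender and race. A method that handles incomplete follow-up is given to two other outcomes: "Implant survival and return to function will be summarized using a Kaplan-Meier method" (Synopsis, repeated in Section XI.A).

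Section VIII.L ends data collection before 5 years if the subject withdraws, is withdrawn by the investigator, "is lost to follow-up, undergoes revision to remove a study device, or expires". Section IX.D.3 ends participation after removal of a component and adds: "This procedure also applies to partial revisions such as polyethylene exchange". Section XI lets the descriptive summaries be used in interim reports, regulatory submissions and publications, and gives no interim schedule. Section XI.B assumes 10% attrition and names no period.

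No denominator is stated for adverse event percentages. The nearest text concerns the primary analysis. Section VI says "Study population for primary statistical analysis will be comprised of males and females who require primary total knee arthroplasty". Section VIII.J says that eligible subjects who consent "but do not undergo the study surgery due to subject withdrawal, investigator withdrawal, or any other reason(s), will be terminated from the study". Of these, and of ineligible subjects in Section VIII.E, the plan says: "These subjects will be excluded from the primary statistical analysis for this study". Together these passages suggest eligible, operated knees.

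**The concern.** Over operated knees, a knee that is lost, withdrawn or not yet at a given time point counts as free of adverse events for time that nobody observed. The percentage then mixes knees followed for weeks with knees followed for years. It belongs to no particular horizon, and it rises from one report to the next even if the underlying risk is constant. The general confidence interval describes sampling error and does not correct this.

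The study has no control arm, so the absolute percentage is the safety result that readers will take away. Perioperative events (Section X.A) are little affected because nearly every knee is observed through that period. Risks that can arise throughout follow-up, such as osteolysis or loosening (Section X.B), are affected most.

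**Working it through.** The plan states no adverse event rate or precision target, so there is no figure of its own to reproduce.

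**Inputs from the plan.** Follow-up is up to 5 years (Section VIII.L). Attrition is 10%, period not given (Section XI.B). The cap is 15 × 100 = 1,500 knees (Synopsis). Section V sets a minimum of six sites, which is 600 knees if each reaches its maximum of 100.

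**Assumptions.** The true five-year risk of a first adverse event is 10%. Operated knees are the base. Loss is unrelated to adverse event risk. All attrition is loss or withdrawal, so death and device removal are not modelled. For interim reports, accrual is uniform over 2 years.

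**End of study.** With constant hazards L for the event and c for loss, the expected crude proportion by time t is

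P(t) = L/(L+c) × [1 − exp(−(L+c)t)].

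- Event hazard: L = −ln(0.9)/5 = 0.02107 per year.
- 10% attrition in total: c = 0.02107, so P(5) = 0.5 × (1 − 0.81) = 9.50%.
- If a share e of the events occurs at the outset, the proportion becomes 0.10e + (1 − 0.10e) × P(5), with L recalculated to keep the five-year risk at 10%. For e = 0.5, L = 0.01081 and the reading is 9.75%. For e = 0.7, L = 0.00656 and it is 9.85%.
- If the 10% were annual, c = 0.10536 and P(5) = (1/6) × (1 − 0.5314) = 7.81% (8.90% and 9.34% with e = 0.5 and 0.7).

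The 95% half-width at 10% is 1.96 × √(0.1 × 0.9/n): 2.4 points at 600 knees and 1.5 at 1,500. The shortfall of 0.15 to 0.5 points under total attrition lies inside both.

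**Interim reports, matched two-year horizon.** The true two-year risk is 1 − exp(−2 × 0.02107) = 4.13%. The crude figure is the mean of P(min(t, 2)) over the follow-up available at the cut, with c = 0.02107.

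| Cut (years from first implant) | Follow-up available (years) | Crude two-year % | Shortfall (points) | Relative shortfall |
|---|---|---|---|---|
| 2 | 0–2 | 2.05 | 2.1 | 50% |
| 3 | 1–3 | 3.55 | 0.6 | 14% |
| 4 | 2–4 | 4.04 | 0.1 | 2% |

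Half-widths at the crude values, for 1,500 and 600 knees, are 0.72 and 1.13 points at 2.05%, and 0.94 and 1.48 at 3.55%. Only the year 2 shortfall exceeds them. With an early-loaded hazard (Weibull shape 0.5, same five-year risk) the relative shortfalls are 33%, 8% and 1%.

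**No defined horizon.** If every event seen so far is counted, as the Synopsis sentence permits, the crude figure at the three cuts is 2.05%, 4.03% and 5.93%, although the hazard never changes.

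**Effect of the remedy.** In 2,000 simulated studies of 1,500 knees with no competing events, one minus Kaplan-Meier averaged 9.99% at the end of the study (crude 9.50%, true 10%). For the two-year risk at the year 3 cut it averaged 4.12% (crude 3.55%, true 4.13%).

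**The case against.** The strongest objection is that the direction of the bias depends on an inferred denominator. The passages pointing to operated knees define the primary analysis, whose endpoint is implant survival. The general rule in Section XI.A could mean percentages per interval among knees seen, which would reduce or change the bias. This stands: a flat statement that the plan understates adverse event risk goes further than the text. What the text does support is that the base and horizon are unstated, and that the reading is low if operated knees are the base.

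A reader might also set a mid-study crude percentage against the five-year risk. With follow-up spread evenly over 0 to 5 years and no loss, the crude figure averages 5.09%, which looks like half of the 10% has gone missing. That comparison is mismatched. Mean follow-up is then 2.5 years, and the true 2.5-year risk is 1 − exp(−2.5 × 0.02107) = 5.13%. Nothing in the plan says an interim percentage will be presented as a five-year risk.

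Two further points limit the concern. Events that lead to device removal are already covered by the Kaplan-Meier survivorship analysis. Death and device removal are competing events rather than unobserved time, so they do not bias a crude proportion over operated knees; only loss, withdrawal and follow-up not yet reached do. Infection, loosening or reoperation that does not end in removal remains without a method that handles incomplete follow-up.

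Finally, this is a descriptive, uncontrolled post-market study, and crude counts are not an error in it. That is fair and bears on severity. Cumulative incidence is itself descriptive, however, and the plan already uses such a method for other outcomes.

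**Conclusion.** The point holds as a minor one. The plan leaves the base and horizon of its adverse event percentages undefined. Over operated knees, they read low for any fixed horizon that not all knees have reached.

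On the assumed 10% five-year risk, the final shortfall is 0.15 to 0.5 points if the 10% attrition is a total, which is within sampling error. It reaches 2.2 points (7.8%) only if the attrition is annual and the hazard constant, and the plan does not say it is annual. In interim reports the two-year shortfall is 2.1 points when the cut falls as a two-year accrual closes, 0.6 a year later and 0.1 a year after that. The sizes rest on the assumed risk, hazard shape and accrual; Section XI permits interim reports but does not schedule them.

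A reader might infer that the final safety result is materially wrong, or that outcome scores share the problem. The documents support neither: the final effect is small at the stated attrition read as a total, and nothing in them establishes a bias in the scores.

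**What to change.** In the Synopsis (Statistical Reporting) and Section XI.A:

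- Name operated knees as the base for adverse event percentages, and keep the counts and percentages.
- Add the cumulative incidence of the first occurrence of a few named key adverse events (for example any serious adverse event, infection, loosening, and reoperation without device removal) at the scheduled visit times, with 95% confidence intervals and numbers at risk.
- Censor at loss, withdrawal or the data cut, and treat death and device removal as competing events.
- Show the numbers at risk in every interim report. In the year 2 cut above, no knee has passed two years, and the numbers at risk would make that plain.

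The cost is some extra analysis and slightly less favourable adverse event figures. The fields of the adverse event form are not in the documents. If it holds no exact dates, timing can be taken to the visit interval, since Section II schedules adverse event reports by visit.
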